**Low-Dose Atropine for Treatment of Myopia**

**PROTOCOL**

**Protocol Identifying Number: MTS1**

**IND Sponsor: Jaeb Center for Health Research, Inc.**

**Version Number: v5.1**

**April 6, 2020**

16 **PROTOCOL AMENDMENT IV (24 Mar 2020)**

17  
18 This amendment provides for the following protocol changes:  
19

20 **Protocol Change # 1**

21  
22 Original Protocol

23 Office visits are conducted at 6, 12, and 18-months post-randomization.  
24

25 Protocol Change

26 A virtual visit may be completed at 6, 12, or 18-months in the event that an in-person office visit  
27 cannot be completed by the participant. Data collected during a virtual visit are a subset of the  
28 data that are collected at an in-office visit (summarized in section 4.9) that can be collected by  
29 means of a phone call, or other smartphone or computer based video/audio method of  
30 communication such as teleconferencing.  
31

32 Rationale for Change and Impact on Study Design

33 Due to the coronavirus (COVID-19) pandemic, participating clinical centers may be unable to  
34 see research participants for in-office study visits in the coming months. The protocol is being  
35 amended to allow for a virtual visit to be completed at 6, 12, or 18-months instead of an office  
36 visit. Given that these visits are prior to the 24-month primary outcome visit, the overall  
37 scientific integrity of the study is maintained.  
38

39 Effect of Change on Informed Consent Form and Study Participants

40 No changes are needed to the current informed consent or assent forms. The data collected by  
41 virtual visit are a subset of the data that would be collected at an in-office visit already described  
42 in the consent form.  
43

44 **Protocol Change # 2**

45  
46 Original Protocol

47 Females who have experienced menarche will undergo a urine pregnancy test at each follow up  
48 visit after randomization. Study medication will be discontinued if the test result is positive.  
49

50 Protocol Change

51 A pregnancy test will be performed at home if an office visit cannot be completed. Pregnancy  
52 testing is being omitted at the 30-month visit which occurs 6 months after study medication has  
53 been discontinued.  
54

55 Rationale for Change and Impact on Study Design

56 Female participants who have experienced menarche must not be pregnant to continue on study  
57 medication. The protocol has been revised to require a pregnancy test to be performed at home  
58 instead of in the office if an in-person office visit cannot be completed by the participant.  
59

60 Effect of Change on Informed Consent Form and Study Participants

61 No changes are needed to the current informed consent form as the form states that pregnancy  
62 tests are required at 6, 12, and 18-months for females who have experienced menarche.  
63

64 **PROTOCOL AMENDMENT III (25 Feb 2019)**

65  
66 This amendment provides for the following protocol changes:

67  
68 **Protocol Change #1**

69  
70 Original Protocol

71 Potential participants with systemic diseases, the specified eye abnormalities, or the inability to  
72 perform study testing were not explicitly excluded from the study.

73  
74 Protocol Change

75 The following items have been added as exclusion criteria in section 2.2.:

- 76 • Diseases known to affect accommodation, vergence, or ocular motility (e.g., multiple  
77 sclerosis, Grave's disease, myasthenia gravis, diabetes mellitus, Parkinson's disease)
- 78 • Existing ocular conditions (e.g., retinal disease, cataracts, ptosis) or  
79 systemic/neurodevelopmental conditions (e.g., Down syndrome) which may influence  
80 refractive development.
- 81 • Any condition that in the judgement of the investigator could potentially influence  
82 refractive development.
- 83 • Existing conditions that may affect the long-term health of the eye or require regular  
84 pharmacologic treatment that may adversely interact with study medication (e.g., JIA,  
85 glaucoma, diabetes mellitus, pre-diabetes).
- 86 • Inability to comprehend and/or perform any study-related clinical tests.

87  
88 Rationale for Change

89 The reasons for excluding certain diseases and/or conditions are specified in the criteria to aid  
90 investigators in understanding the exclusions. The inability to comprehend and/or perform any  
91 study-related clinical tests by a potential participant would prevent the study from collecting  
92 necessary valid and complete data.

93  
94 **Protocol Change #2**

95  
96 Original Protocol

97 Section 4.1 includes the following two statements:

- 98 • A central pharmacy will *compound* the atropine and placebo eyedrops based on a participant-  
99 specific treatment group and will package them in identical single-use ampules to maintain  
100 masking.
- 101 • The atropine eyedrops will consist of 0.01% atropine. The placebo eyedrops will consist of  
102 0.5% hydroxypropol methylcellulose and 1:10,000 benzalkonium chloride.

103  
104 Protocol Change

105 A separate section 4.1 has been added to better describe Study Medication.

106  
107 Nevakar is manufacturing the study drug (0.01% atropine) and placebo and packaging both in  
108 identical-appearing single-use ampules. In addition to 0.01% atropine, the ampules contain a  
109 buffer similar to artificial tears while the placebo contains just the buffer similar to artificial  
110 tears. The atropine and placebo ampules are sent to a central pharmacy, which will label and

111 package multiple atropine or placebo ampules into three month supply packages to maintain  
112 masking. The packages of ampules will be shipped to participating sites in insulated shipping  
113 boxes designed to maintain study drug at 59 to 77 degrees F during shipping. Participating sites  
114 will store study drug at room temperature (between 68 and 77 degrees F) prior to dispensing  
115 study medication packages to study participants. Additional study medication details are  
116 summarized within a separate investigational product manual.

117  
118 Rationale for Change

119 The terms “compound” and “1:10,000 benzalkonium chloride” were inadvertent holdovers from  
120 a previous draft protocol that was written when the study was expected to use a compounding  
121 pharmacy to produce the atropine eyedrops. No compounding or preservative is needed for the  
122 study medication currently manufactured in single-use ampules (monitored by US FDA) which  
123 are shipped directly from the manufacturer.

124  
125 **Protocol Change #3**

126  
127 Original Protocol

128 Section 4.3 on phone calls stated that “Two weeks following randomization ( $\pm 3$  days), the site  
129 will contact parents *to confirm receipt of study medication* and question the parent as to whether  
130 the child is experiencing any issues with treatment.”

131  
132 Protocol Change

133 The phrase “to confirm receipt of study medication” has been omitted.

134  
135 Rationale for Change

136 There is no need to confirm receipt of study medication on the 2-week phone call because study  
137 medication is handed directly to participants at their office visit at the time of randomization.  
138 The “*to confirm receipt of study medication*” wording was an inadvertent holdover from a  
139 previous draft protocol which was written when the study was expected to mail study medication  
140 to participants.

141  
142 **Protocol Change #4**

143  
144 Original Protocol

145 Although a negative urine pregnancy test is required for enrollment of any female who had  
146 reached menarche, no pregnancy testing was described during follow up.

147  
148 Protocol Change

149 A pregnancy test is now required at every post-randomization follow up visit for females who  
150 have experienced menarche.

151  
152 Rationale for Change

153 Pregnancy testing during post-randomization follow up (section 4.9) was felt necessary to  
154 enforce the existing requirement that study medication be discontinued in the event of pregnancy  
155 during the study.

156  
157 **Protocol Change #5**

158  
159 Original protocol

160 One inclusion criteria for randomization was interocular difference  $\leq 0.1$  logMAR ( $\leq 5$  letters  
161 by E-ETDRS testing).

162

163 Protocol change

164 This inclusion criteria has been changed to interocular difference  $\leq 0.2$  logMAR ( $\leq 10$  letters  
165 by E-ETDRS testing) in sections 1.11, 1.12, and 3.4.

166

167 Rationale for Change

168 The intent of the exclusion criteria for interocular difference was to exclude children with  
169 amblyopia; however, the previous interocular difference of 0.1 (5 letters) is within test-retest  
170 variability for E-ETDRS visual acuity testing. The criteria was expanded to allow enrollment of  
171 children with interocular differences up to 0.2 logMAR (10 letters), the threshold that is used to  
172 define amblyopia in several other PEDIG studies of intermittent exotropia.

173

174

175

176 **PROTOCOL AMENDMENT II (12 Jun 2018)**

177  
178 This amendment provides for the following protocol changes:  
179

180 **Protocol Change #1**

181  
182 Original Protocol

183 It was not an inclusion criterion that participants were required to have excellent compliance  
184 with spectacle correction either to be enrolled into the run-in phase or to be eligible for  
185 randomization. Participants who were not currently wearing refractive correction were eligible  
186 for the study and could have spectacle correction initiated during the run-in phase.  
187

188 Protocol Change

189 Excellent compliance with refractive correction (76% to 100% of waking hours) for at least one  
190 month will be an eligibility criterion for enrollment into the run-in phase (sections 1.11, 1.12,  
191 and 2.2). Similarly, excellent compliance with refractive correction during the run-in phase will  
192 be encouraged and will be required to be eligible for randomization (sections 1.11, 1.12, 2.5, 2.6,  
193 3.2, 3.3, and 3.4).  
194

195 Rationale for Change

196 It is not known whether spectacle compliance could interact with the effect of atropine eyedrops,  
197 but limiting the study to children who are compliant with refractive correction will guard against  
198 the possibility of having lowered statistical power for analysis should such an interaction exist.  
199 It was also felt that children who are compliant with refractive spectacle correction might also be  
200 more likely to be compliant with nightly eyedrops for two years than children who are not  
201 compliant with refractive correction. It is acknowledged that the study results will be  
202 generalizable only to children who are compliant with refractive correction.  
203

204 **Protocol Change #2**

205  
206 Original Protocol

207 The original protocol indicated that “It is the investigators’ opinion that the protocol’s level of  
208 risk falls under DHHS 46.404, which is research not involving greater than minimal risk.”  
209 (section 6.4.3)  
210

211 Protocol Change

212 The revised protocol states that “The Jaeb Center Institutional Review Board has classified the  
213 protocol as research involving greater than minimal risk using the federal definition under 45  
214 CFR 46.102i.”  
215

216 Rationale for Change

217 The protocol was assigned the risk level of “research involving greater than minimal risk” by the  
218 Jaeb Center for Health Research Institutional Review Board when it approved the protocol.  
219

220 **Protocol Change #3**

221 Original Protocol

222 Mean corneal radius was one of the biometric parameters to be measured. Three summary  
223 measurements of axial length, mean corneal radius, anterior chamber depth and lens thickness  
224 were to be taken using an optical biometer (e.g. IOLMaster, LENSTAR).

225  
226 Protocol Change

227 Flat corneal radius will be measured instead of mean corneal radius because that is what both optical  
228 biometers can measure. The first summary measurement of axial length, flat corneal radius, anterior  
229 chamber depth and lens thickness will be collected, with each value based on the individual  
230 instrument's method of taking and then averaging multiple measures.

231  
232 Rationale for Change

233 For corneal curvature, the only common measurement and unit of measure for the two optical  
234 biometers being used is flat corneal radius and diopter. To avoid increasing the testing burden  
235 for participants, a single measurement was deemed sufficient for these four biometric  
236 parameters.

237  
238 **In addition, the following minor corrections/clarifications have been made.**

- 239
- 240 • Typos were corrected in protocol change #1 in protocol amendment I and in section 7.4.2 to  
241 reflect that near visual acuity is measured binocularly, not in each eye.  
242
  - 243 • Clarification that the *average* spherical equivalent between eyes is used for the primary  
244 analysis of myopia progression (section 1.1)  
245
  - 246 • In section 3.4 concerning eligibility for randomization, clarified that participants who do not  
247 meet eligibility criteria will be withdrawn from the study *without being randomized*.  
248
  - 249 • Clarified in section 6.4.2 that it refers to the *24-month* primary outcome in the section  
250 pertaining to participants develops adverse effects serious enough to discontinue study  
251 medication.  
252
  - 253 • The enrollment visit has been added to the list of visits that are paid for by the study (section  
254 5.4); it was originally omitted in error.  
255
  - 256 • In section 7.1.1 regarding the 24-month on-treatment primary analysis
    - 257 ○ Clarified that adjustment covariates are included to improve power for the treatment  
258 group comparison, as well as to account for potential residual confounding  
259 Clarified that baseline spherical equivalent refractive error (SER) will be included in the  
260 analysis model as an adjustment factor, while the change in SER at all follow-up visits  
261 up to and including the 24-month visit will be included in the longitudinal outcome  
262 vector. Further details, including handling of missing data, will be included in the  
263 separate Statistical Analysis Plan.  
264
  - 265 • Section 7.6 has been updated based on recent decision from the Data Safety and Monitoring  
266 Committee that evaluation of whether an interim monitoring is needed would be made after 6  
267 months of recruitment and before any outcome data are reviewed.  
268

- 269 • In Section 6.4.2, clarified that the reason for trying progressive lenses is to address adverse  
270 events related to near focusing problems.  
271
- 272 • In the statistical analysis chapter, a few minor corrections have been made to the data for two  
273 previous studies (CLEERE and ATOM2) that are cited as background data for estimating  
274 sample size (sections 7.8.2. 7.8.3). Note that none of these minor changes affected the sample  
275 size calculation.  
276
- 277 • In section 7.8.5, a few minor corrections have been made to the numbers in Table 2 on the  
278 expected width of confidence intervals on the treatment group comparisons of myopia  
279 progression in racial subgroups. None of these minor changes were substantive.  
280
- 281 • In section 7.8.1, the purpose of the general considerations for sample size section was  
282 clarified. In addition, two sentences were omitted here as they were already covered  
283 elsewhere in section 7.8.  
284
- 285 • In section 2.4, some details of the cycloplegic autorefraction and other biometry  
286 measurements have been omitted and moved to a separate manual of procedures.  
287

288  
289  
290  
291  
292  
293  
294  
295  
296  
297  
298  
299  
300  
301  
302  
303  
304  
305  
306  
307  
308  
309  
310  
311  
312  
313  
314  
315  
316  
317  
318  
319  
320  
321  
322  
323  
324  
325  
326  
327  
328  
329  
330  
331  
332  
333  
334

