#### 1121 **4.8 Follow-up Visit Schedule in Randomized Trial**

1122 The follow-up visit schedule consists of the following office visits timed from randomization:

- 1123 • 6 months  $\pm$  2 weeks\*
- 1124 • 12 months  $\pm$  2 weeks\*
- 1125 • 18 months  $\pm$  2 weeks\*
- 1126 • 24 months  $\pm$  4 weeks: On-Treatment Primary Outcome – discontinue treatment after visit
- 1127 • 30 months  $\pm$  4 weeks: Off-Treatment Secondary Outcome – six months following  
1128 discontinuation of treatment

1129  
1130 \*A virtual visit may be completed at 6, 12, or 18-months if an in-person office visit cannot be  
1131 completed by the participant. If any safety events are identified during a virtual visit, participants will  
1132 have additional follow up as applicable.  
1133

1134 Additional visits may be scheduled at investigator discretion. Adverse event data may be reported  
1135 and collected at any time during the study.  
1136

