#### 1137 **4.9 Follow-up Visit Testing Procedures**

1138 At each office visit the following tests and assessments will be done with the participant wearing  
1139 their current refractive correction:  
1140

- 1141 1. Medical History - including questioning about the occurrence of adverse effects of treatment.  
1142 Concomitant medications will be recorded, as well as current eyeglasses or contact lenses  
1143 correction.
- 1144 2. Compliance Assessment
  - 1145 • All unused study medication ampules since the last visit (if brought to the visit) will  
1146 be counted as a measure of compliance.
  - 1147 • Home calendar logs (if brought to the visit) will be reviewed and assessments of  
1148 compliance with eyedrops and with refractive correction will be recorded on the  
1149 Follow-up Examination Form

- 1150 3. Eye Drop Questionnaire (all follow up visits except the 30-month visit)  
1151 • To be completed by the child prior to any other testing to evaluate the effect of eye  
1152 drops on the child.
- 1153 4. Distance Visual Acuity Testing (30-month visit only): Monocular distance visual acuity  
1154 tested at the start of the exam without cycloplegia in current correction.  
1155 • Measurement of best corrected visual acuity in each eye by a study certified visual  
1156 acuity tester using the E-ETDRS testing protocol.  
1157 • If the vision is more than one line ( $\geq 5$  letters) worse than baseline, retest using trial  
1158 frames or phoropter with the most recent subjective refraction.
- 1159 5. Binocular Near Visual Acuity Testing (6-month visit only): Binocular near visual acuity is  
1160 measured using the ATS4 Near Acuity Test with participant wearing current refractive  
1161 correction prior to administration of cycloplegia.
- 1162 6. Binocular Amplitude of Accommodation: Measured in their current correction without  
1163 cycloplegia with a study-specified and provided accommodation near-point rule (e.g.  
1164 Gulden's near-point rule).
- 1165 7. Standard Refraction  
1166 • The investigator may use their standard refraction technique (with or without  
1167 cycloplegia) at any time during the visit to ensure that refractive correction meets  
1168 study criteria at each visit (see section 4.9 below).  
1169 • At 30-month visit, only required if the vision is more than one line ( $\geq 5$  letters)  
1170 worse than baseline.
- 1171 8. Following cycloplegia, at all visits an examiner masked to treatment group will perform:  

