1172 • Cycloplegic Autorefraction – (see section 2.4)  
1173 • Cycloplegic Axial Length Measurement and Additional Biometry (see section 2.4)  
1174

1175 If a virtual visit is completed, only items 1 through 3 above will be completed. If any safety events  
1176 are identified during a virtual visit, participants will have additional follow up as applicable.  
1177

1178 In addition, females who have experienced menarche will undergo a urine pregnancy test at each  
1179 follow up visit except the 30-month visit (or at home if a virtual visit is completed).  
1180

- 1181 • In the case of pregnancy during the study, study eyedrops will be discontinued although  
1182 the subject will be retained in the study.  
1183

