#### 1184 **4.10 Management of Refractive Error**

1185 Spectacle or contact lenses correction must be updated whenever the investigator's standard  
1186 refraction technique reveals a change in refractive error. A change in refractive error is defined  
1187 as any of the following amounts:  
1188

- 1189 • A difference of  $\geq 0.75$  D sphere
- 1190 • A difference of  $\geq 0.75$  D cylinder
- 1191 • A difference of  $\geq 0.50$  D in SE anisometropia
- 1192 • A difference in axis of 6 degrees or more when the cylinder is  $\geq 1.00$  D.  
1193

1194 Whether to update the correction for smaller differences in refraction is at investigator discretion.  
1195 Glasses required by a contact lens user should be updated when their contact lenses are updated,  
1196 and these glasses will be paid for by the study.

1197  
1198 If updated, the refractive correction must meet the requirements described in section 2.5.  
1199  
1200 Daily wear single vision contact lenses may be used for correction of refractive error full time or  
1201 alternating with spectacle correction. Contact lenses should not differ from a cycloplegic over-  
1202 refraction by more than +/- 0.50D SE. Uncorrected astigmatism should not exceed 1.00D.  
1203 OrthoK, rigid gas permeable, and other contact lenses being used to affect myopia progression  
1204 are not allowed. Contacts must be removed from the eyes prior to study medication  
1205 administration and not reinserted for at least 30 minutes.  
1206

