#### 1459 **7.1.2.2 Change in Axial Length at 12 and 24 Months**

1460 Axial length will be reported as the distributions of baseline length, 12-month length, 24-month  
1461 length, and change in axial length from baseline to 12 and 24 months. A treatment group  
1462 comparison of the change from baseline to 12 months and 24 months in axial length will be  
1463 performed using a longitudinal discrete time mixed model, which allows for interaction between  
1464 time and treatment group, and adjusts for baseline axial length, age, iris color (brown vs. non-  
1465 brown) and East Asian vs. non-East Asian race. At baseline and all follow-up visits, including  
1466 the 12 and 24-month visits, the mean of the axial length readings in both eyes for each  
1467 participant will be used for the analysis. The treatment group difference (atropine – placebo) and  
1468 a 95% confidence interval will be calculated based on the model estimates at 12 months and 24  
1469 months.

1470

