#### 1487 **7.1.3.1 Refractive Error at 12 Months**

1488 The model used for the primary analysis at 24 months will also be used to perform a treatment  
1489 group comparison of change from baseline to 12-months in spherical equivalent refractive error  
1490 (SER), as measured by a masked examiner using cycloplegic autorefraction.

1491

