### **7.3.2 Treatment Effect over Time**

The treatment effect on change in spherical equivalent refractive error (SER) from baseline through the first year will be compared with the treatment effect on change in SER from end of first year through the second year, by constructing the appropriate contrasts in the primary analysis model.

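### A virtual 12-month visit drops the masked refraction and axial-length exam with no required catch-up, although three declared 12-month secondary outcomes need it

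*Protocol*

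**What the plan says.** - **Rationale.** Amendment IV, Protocol Change #1, argues "Given that these visits are prior to the 24-month primary outcome visit, the overall" integrity of the study is maintained. The passage on impact does not mention the 12-month outcomes.
- **Rule in the current text.** Section 4.8: "A virtual visit may be completed at 6, 12, or 18-months if an in-person office visit cannot be" completed by the participant. Section 1.11 carries the same footnote.
- **Content of a virtual visit.** Section 4.9: "If a virtual visit is completed, only items 1 through 3 above will be completed". Items 1 to 3 are medical history, compliance and the eye drop questionnaire. Item 8 is the outcome exam: "Following cycloplegia, at all visits an examiner masked to treatment group will perform" cycloplegic autorefraction, axial length and other biometry.
- **What follows a virtual visit.** Sections 4.8 and 4.9 call for additional follow-up when a safety event is found. Other extra visits are left to the investigator. The window is ±2 weeks at 6, 12 and 18 months and ±4 weeks at 24 and 30 months.
- **Outcomes that need the month-12 exam.** Section 7.1.2.2: "Axial length will be reported as the distributions of baseline length, 12-month length, 24-month" length and change to both times. Section 7.1.3.1: "The model used for the primary analysis at 24 months will also be used to perform a treatment" group comparison of SER change at 12 months. Section 7.1.3.2 adds progression of at least 1 D at 12 months, by a Cox model. Section 7.3.2: "The treatment effect on change in spherical equivalent refractive error (SER) from baseline" through year 1 is compared with the effect in year 2.

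**The concern.** The amendment treats the three intermediate visits as expendable because they come before month 24. Section 7 does not: three secondary outcomes and one planned contrast rest on month-12 measurements that a virtual visit leaves out.

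Some of these exams will be impossible at the nominal date but possible some weeks later. The protocol neither asks for the late exam nor gives it a window. Whether it is done is then left to each investigator, and a late value has no defined place in the 12-month comparison. An analysis plan can model a missing value, but it cannot order an exam. The rule on catching up therefore belongs in the protocol's visit schedule.

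At stake are the precision of the declared 12-month results and a very small count of children reaching 1 D by month 12.

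**Working it through.** **Plan's own figure.** Section 7.8.3 sizes the trial on a 0.50 D difference at 30 months, SD 0.90 D, 90% power and 2:1 allocation. A t-test calculation gives 156 evaluable children (104:52), power 0.902. Allowing 15% loss, 52/0.85 = 61.2, rounded up to 62 placebo and doubled to 124 atropine, total 186. This agrees with the protocol, and the present point does not affect it.

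**Text side by side.**

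| 12-month analysis | Measurement needed | Done at a virtual visit? |
|---|---|---|
| SER change (7.1.3.1) | cycloplegic autorefraction, item 8 | no |
| Axial length change (7.1.2.2) | optical biometry, item 8 | no |
| Progression of at least 1 D (7.1.3.2) | cycloplegic autorefraction, item 8 | no |
| Year 1 versus year 2 (7.3.2) | SER at months 12 and 24 | month 12 not measured |

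**Size: assumptions.** The share p of virtual 12-month visits is unknown; 20% and 30% are used. The 12-month SDs are 0.44 D (control arm of the earlier 1% atropine trial) and 0.52 D (0.01% arm of the later dose trial), both from Table 1 in section 1.4. The correlation between 12- and 24-month change is assumed to be 0.71–0.85. Month 24 is taken as observed, and missing exams as missing at random.

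**12-month SER, mixed model.** If the exams still present explain a fraction R² of the variance at month 12, the standard error is multiplied by √[1 + (1 − R²)·p/(1 − p)].
- Only month 24 present, correlation 0.71: R² = 0.504. At p = 0.2, √(1 + 0.496 × 0.25) = 1.060. At p = 0.3, √(1 + 0.496 × 0.429) = 1.101.
- Months 6, 18 and 24 all present, R² taken as about 0.79: √(1 + 0.21 × 0.25) = 1.026 and √(1 + 0.21 × 0.429) = 1.044.

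The rise is therefore about 3–6% at 20% virtual and 4–10% at 30%.

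**Year contrast.** This is twice the 12-month change minus the 24-month change. In the same type of model its standard error rises by about 8–12% at 20% and 13–20% at 30%, because month 24 says little about how the change was split between the years.

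**Available cases only, as an outer limit for SER.** With SD 0.52 D, 124:62 children and a difference of 0.25 D (half of 0.50 D), the 95% half-width with none missing is 1.973 × 0.52 × √(1/124 + 1/62) = 0.160 D, power 87%. At 20% missing it is 0.179 D and 78%; at 30%, 0.191 D and 73%. The planned mixed model does better than this.

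**Progression of at least 1 D.** With 12-month means of 0.50 D (placebo) and 0.25 D (atropine), half the 24-month planning values, and normal tails:
- Placebo: 62 × P(Z > 0.50/0.44) = 7.9, to 62 × P(Z > 0.50/0.52) = 10.4.
- Atropine: 124 × P(Z > 0.75/0.44) = 5.5, to 124 × P(Z > 0.75/0.52) = 9.3.

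If every child with a virtual visit were lost to this outcome, the standard error would rise by 1/√(1 − p) − 1, which is 12% at 20% and 20% at 30%. That is an upper bound, for the reason given under the objection.

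**The case against.** **The comparator.** The virtual visit applies only when the child cannot attend. The alternative is then a missed visit, not an exam, and the call adds safety and compliance data. This stands: allowing virtual visits was sensible, and limiting them to site closures could cost safety contacts. The weakness is only that the exam lapses with no required catch-up.

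**The integrity sentence.** It speaks of overall integrity and ties it to the primary outcome, which remains in person. It is defensible for that outcome and incomplete for the 12-month ones.

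**The analysis plan.** Handling of missing and late values can sit there. Requiring the exam and setting its window cannot.

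Four stronger readings are tempting, but the document does not support them.
- *There is no later exam.* The 18-month exam remains unless it too is virtual, the 24-month exam remains, and discretionary visits are allowed. What is absent is a required catch-up.
- *Nothing is recovered for progression of at least 1 D.* Section 7.1.3.2 uses a Cox model, so the 6-month exam still contributes. Neighbouring exams often settle the status: in a simulation with assumed 12-month SD 0.46–0.51 D and correlation 0.77–0.91, the 6- and 18-month exams bracketed it for about 66% of placebo and 84% of atropine children when only month 12 was missing.
- *The missing exams depend on how families feel treatment is going.* Families are masked and the stated trigger is inability to attend, so this is speculation.
- *Section 4.10 is contradicted.* It begins "Spectacle or contact lenses correction must be updated whenever the investigator's standard" refraction shows a change. It does not demand a refraction at every contact.

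**Conclusion.** The point holds as a gap in the visit rules, and it should be corrected. As written, the protocol keeps three 12-month secondary outcomes and a year-1 versus year-2 contrast while letting the exam they rest on lapse without a required replacement. The stated justification reaches the primary outcome only.

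The harm is moderate and confined mainly to month 12. With 20–30% of 12-month visits virtual, the standard error of the 12-month SER difference rises by roughly 3–10%. For progression of at least 1 D the rise is at most 12–20%, on roughly 8–10 expected placebo and 5–9 atropine events. These figures rest on an assumed share of virtual visits, assumed correlations, month 24 being attended and missingness at random. A reader might go on to infer that the 24-month result is compromised. The document does not support that, because the primary outcome is still measured in the office by a masked examiner.

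**What to change.** 1. In 1.11, 4.8 and 4.9, keep the virtual visit as a safety and compliance contact whenever an office visit cannot be completed, and record the reason.
2. State that item 8 is deferred, not waived. It is done in the office as soon as the child can be seen, within a stated widened window that closes before the next scheduled exam, and the actual date is recorded.
3. Leave the prespecified discrete-time primary model unchanged. Use late values in the 12-month secondary comparisons with adjustment for actual exam time, or in a sensitivity analysis.
4. Amend the integrity statement to say that the 12-month secondary outcomes are affected.

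**Cost.** Protocol wording and a time adjustment in secondary analyses. The exam is one already planned, so no new procedure is added. Some families make an extra trip, some 12-month values will be late, and the gain for 12-month SER is modest when the neighbouring exams are present.
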